## Study information

Title	Real World Evidence study of Danish Fabry patients: a >20-year longitudinal retrospective analysis of prospectively collected data.
Protocol version identifier	V1
Date of last version of protocol	
Active substance	NA
Medicinal product	NA
Product reference	NA
Procedure number	
Marketing authorisation holder(s)	
Joint PASS	
MAH(s) contact	
Research question and objectives	
Research Question
 
Is the incidence and prevalence of Fabry associated clinical events (FACEs) (cardiac, renal and cerebrovascular) associated with sex, genotype, phenotype at time of diagnosis, biomarkers, and Fabry specific therapy?
 
Objectives
 
To investigate time to first Fabry associated clinical events (FACEs) (cardiac, renal, and cerebrovascular) with particular focus on Migalastat clinical outcomes and treatment outcomes preceding Migalastat therapy.
 
To investigate the incidence and prevalence of FACEs with respect to Fabry specific treatment, Migalastat, ERT or no treatment.
 
To describe FACEs in accordance with different geno- and phenotypic groups.
 
To investigate the incidence and time to a first fatal or non-fatal cardiac, renal and cerebrovascular clinical event, separated by each category.

Title	Real World Evidence study of Danish Fabry patients: a >20-year longitudinal retrospective analysis of prospectively collected data.
	
Primary objectives
 
To investigate time to first Fabry associated clinical events (FACE) (cardiac, renal, and cerebrovascular) with particular focus on Migalastat clinical outcomes and treatment outcomes preceding Migalastat therapy.
 
Secondary objectives
 
To investigate the incidence and prevalence of FACEs with respect to Fabry specific treatment, Migalastat, ERT or no treatment.
 
To describe FACEs in accordance with different geno- and phenotypic groups.
 
To investigate the incidence and time to a first fatal or non-fatal cardiac, renal and cerebrovascular clinical event, separated by each category.
 
.

Country(-ies) of study	Denmark

## **STATEMENT OF COMPLIANCE**

The study will be conducted in accordance with the Declaration of Helsinki principles, International Conference on Harmonisation (ICH) Good Clinical Practice (GCP) guidelines, and applicable Danish regulations and laws. All personnel involved in the conduct of this study have completed human subjects' protection training.

## List of abbreviations

α-Gal A	Alpha Galactosidase A
ACE	Angiotensin-Converting Enzyme
ARB	Angiotensin-Receptor Blockers
BPI	Brief Pain Inventory
CRA	Clinical Research Assistant
CRO	Contract Research Organization
eCRF	electronic Case Report Form
EDC	Electronic Data Capture
ERT	Enzyme Replacement therapy
ESRD	End-Stage Renal Disease
FACE	Fabry Associated Clinical Event
FPI	First Patient In
GL-3/Gb3	Globotriaosylceramide
Lyo Gb3	Globotriaosylsphingosine
GCP	Good Clinical Practices
GLA	Galactosidase A
IgG	Immunoglobulin G
LPO	Last Patient Out
LV	Left Ventricle
LVH	Left Ventricular Hypertrophy
LVMI	Left Ventricular Mass Index
MedDRA	Medical Dictionary for Regulatory Activities
MSSI	Mainz Severity Score Index
PBI	Patient Benefit Index
PBQ	Patient Benefit Questionnaire
PCA	Principal Component Analysis
PI	Principal Investigator
PNQ	Patient Needs Questionnaire
PT	Preferred Term
Q1	First Quartile
Q3	Third Quartile
SF-36v2	The Short Form (36) Health Survey version 2
SIV	Site Initiation Visit
SmPC	Summary of Product Characteristics
SOC	System Organ Class
TSQM-9	Treatment Satisfaction Questionnaire for Medication v.9
QoL	Quality of Life
SAE	Serious Adverse Event

## Abstract

Title	Real World Evidence study of Danish Fabry patients: a > 20-year longitudinal retrospective analysis of prospectively collected data.
Rationale and background	
Fabry is a rare X-linked metabolic lysosomal disorder caused by deficiency in the enzyme <math>\alpha</math>-galactosidase A (<math>\alpha</math>-Gal A) by mutations in the GLA gene, encoding the <math>\alpha</math>-Gal A enzyme, which catalyses glycosphingolipids, namely globotriaosylceramide (Gb3). Reduced or absent <math>\alpha</math>-Gal A activity leads to accumulation of Gb3 in various organs as well as cellular dysfunction and inflammation causing physical symptoms and eventual organ failure. Migalastat, an oral chaperone therapy was approved for Fabry patients in 2016 providing an alternative to infusions with enzyme replacement every 2 weeks. Although the initial trials of Migalastat had some both short and extended outcome treatment comparisons, the overall evidence of clinical efficacy is based on too small numbers considering the heterogeneity of the Fabry patient population as well as the very slow progression of the disease. Though the body of real-world evidence is growing, there is a need for more publications of real-world long-term data on clinical outcomes with a focus on treatment with Migalastat.

Research question and objectives	
Research Question
 
Is the incidence and prevalence of Fabry associated clinical events (FACEs) (cardiac, renal, and cerebrovascular) associated with sex, genotype, phenotype at time of diagnosis, biomarkers, and Fabry specific therapy?
 
Objectives
 
To investigate time to first Fabry associated clinical events (FACE) (cardiac, renal, and cerebrovascular) with particular focus on Migalastat clinical outcomes and treatment outcomes preceding Migalastat therapy.
 
To investigate the incidence and prevalence of FACEs with respect to Fabry specific treatment, Migalastat, ERT or no treatment.
 
To describe FACEs in accordance with different geno- and phenotypic groups.
 
To investigate the incidence and time to a first fatal or non-fatal cardiac, renal, and cerebrovascular clinical event, separated by each category.
 
Primary outcomes
 
Time to first FACE (cardiac, renal, and cerebrovascular) with particular focus on Migalastat on clinical outcomes and treatment outcomes preceding Migalastat therapy.

	
Secondary outcomes
 
To investigate the incidence and prevalence of FACEs with respect to Fabry specific treatment, Migalastat, ERT or no treatment.
 
To describe FACEs in accordance with different geno- and phenotypic groups
 
To investigate the incidence and time to a first fatal or non-fatal cardiac, renal and cerebrovascular clinical event, separated by each category.

Study design	Retrospective observational, single-center study from the Danish National Fabry Center. Describing treatment related outcomes in Fabry Disease over time.
Population	
 
• Male and female patients with a diagnosis of Fabry Disease.
 
• Registered at the Danish National Fabry center, Rigshospitalet, Denmark from 01.01.2001.
 

Variables	
The primary endpoint is time to first FACE (cardiac, renal, or cerebrovascular events) since each baseline, with particular focus on the added value of the recent addition of Migalastat as a treatment option.
 
Secondary endpoints are prevalence and incidence of FACEs and time to first FACE.
 
Exploratory endpoints: Organ-specific biomarkers across modalities (auditory, lung, heart, kidney, skin, and neurological), and patient-reported outcomes evaluated by questionnaires.

Data sources	Electronic medical records and paper records.
Study size	Estimated 115 patients, which constitute all patients with a genetically verified diagnosis of Fabry disease in Denmark.
Data analysis	
Primary endpoint will be addressed using event-driven statistics from a baseline based on the date of diagnosis and treatment initiation.
 
Secondary analyses will address the individual parameters of the FACEs.
 
Exploratory endpoints will rely on repeated measures statistical models to investigate the change in organ-specific function during the 20-year follow-up. Detailed description is found in statistical analysis plan (SAP).

Milestones	
Ethics Committee Approval	Q3 2023
Start of data collection	Q3 2023
End of data collection	Q1 2024
Study progress report	Q1 2024
Interim report (baseline data)	Q2 2024

Registration in the EU PAS register	Q3-4 2023
Final report of study results	Q3 2024

## **Amendments and updates**

None

## Milestones

Milestone	
Ethics Committee Approval	Q3 2023
Start of data collection	Q3 2023
End of data collection	Q1 2024
Study progress report	Q1 2024
Interim report (baseline data)	Q2 2024
Registration in the EU PAS register	Q3-4 2023
Final report of study results	Q3 2024

## **Rationale and background**

Fabry disease is a rare X-linked lysosomal disorder in lysosomes, resulting in a multisystemic disorder caused by deficiency in the enzyme  $\alpha$ -galactosidase A ( $\alpha$ -Gal A) due to mutations in the GLA gene, encoding the hydrolase  $\alpha$ -Gal A enzyme, which catalyses glycosphingolipids namely globotriaosylceramide (Gb3). Reduced or absent  $\alpha$ -Gal A activity leads to accumulation of Gb3 in the lysosomes of various organs, as well as cellular dysfunction and inflammation causing physical symptoms and eventual organ failure (1,2). Fabry disease as an X-linked disorder with a high penetrance, though not 100% in female heterozygotes, although the disease affects both males and females. With the X-linked nature, Fabry disease is suitable for an efficient, high diagnostic yield cascade screening over at least three generations surrounding an index-patient. The Danish National Fabry Centre has now more than 20 years of experience of cascade screening, which has provided a patient population of 115 male and female patients. The prevalence of Fabry disease in the Danish population is estimated to be 1:58000 (males 1:85000, females 1:44000) (3).

Primarily male patients, with early onset classical phenotypes have none or very low  $\alpha$ -Gal A activity, and they inevitably develop multiorgan failure without treatment (4). Patients with late onset of Fabry disease represent both males and females with higher  $\alpha$ -Gal A activity and variable degrees of organ involvement (5). Fabry disease can cause irreversible damage to multiple organs resulting in Fabry associated clinical events (FACEs) such as renal, cardiac, cerebrovascular events, and death (5).

The primary Fabry specific therapy has historically been enzyme replacement therapy (ERT), and as of 2016 an oral chaperone therapy, Migalastat, has been available, providing an alternative to ERT for patients with amenable mutations by increasing their endogenous  $\alpha$ -Gal A enzyme activity (6–14). However, real-world long-term data from well-characterised cohorts with available detailed clinical consecutive observations with focus on treatment with Migalastat and Fabry associated events has not been fully investigated (12–14).

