#### Demographics

Date of Birth	• DDMMYYYY
Sex	• Male • Female
Ethnicity	White Black Asian

	Others
City	Residence City

Fabry-specific disease background

Age of first symptoms	Years
Age of diagnosis	Years
Fabry family history	Yes No Unknown
Index case	Yes No
ALPHA GAL ACTIVITY (LEUCO ASSAY) at inclusion	% of normal activity
MOLECULAR TEST	Amenable mutation found: Other mutations

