4. SAMPLE SIZE JUSTIFICATION

Approximately 115 patients with established Fabry Disease, estimated 2/3 female and 1/3 male.

Sample size was not determined statistically. All patients from Danish National Fabry Centre are included.

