13. ANALYSIS OF EFFECTIVENESS

13.1. Primary Endpoint

The comparison of interest is between migalastat-treated and untreated patients in the Primary and Secondary Effectiveness Populations. The analysis for the primary effectiveness endpoint will be performed at the 2-sided significance level of 0.05. This analysis will be performed when enough data are available.

Clinical effectiveness will be based on FACEs of cardiac, cerebrovascular, and renal events, and deaths due to FACEs. A composite event is defined as the occurrence of either cardiac, cerebrovascular, or renal clinical event, and death due to FACEs.

Subject matter experts will adjudicate all reports of FACEs. For all summary analyses, the adjudicated decisions will be used if they differ from the initial report. Both original and adjudicated decisions will be reported in listings. Only adjudicated decisions will be used for analyses.

Analyses will be performed in the Primary and Secondary Effectiveness Population.

The analyses described further in Section **Error! Reference source not found.** through Section **Error! Reference source not found.** will be performed for the endpoint of all FACEs combined and separately for all specific FACEs categories listed above (including deaths in these categories) as supportive analyses. A separate analysis of all deaths due to FACEs will also be conducted.

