13.1.1. Cox Proportional Analysis for Fabry-associated Clinical Events

The time to the first event is defined as time from the Analysis Start Date to the first composite FACE (primary interest), and to the first cardiac, cerebrovascular, renal clinical event, or death due to FACEs. For the primary analysis, patients who complete the study without an event, are lost to follow-up, discontinued the study, started dialysis, had a kidney or heart transplant, or after 30 days they changed/switched therapy (migalastat group) or after they start therapy (untreated group) will be censored. Describing effectiveness in migalastat treated population is of the main interest.

Treatment Switch

The primary analysis will address events that occur on therapy from the Analysis Start Date up until 30 days after the patient stops therapy or switches therapy. The events that happen afterwards will be excluded. For the patients untreated at time of diagnosis, the primary analysis will address events from the time of diagnosis until the patient starts a therapy. The events that happen afterwards will be excluded. An additional analysis will be performed:

1. An analysis that will address events that occur on therapy from the time of Analysis Start Date up until the patient stops therapy or patient switches therapy. For the untreated patients, the analysis will address assessments from the time of diagnosis until the patient starts a therapy. The events that happen afterwards will be excluded.

Primary Analysis Method

The ratio of the hazards of treatment groups will be checked to ensure that the hazard ratios are constant over time. Secondly, the assumption that each variable in the model makes a linear contribution will be checked.

The covariates will include:

- sex
- age at the Analysis Start Date as a continuous variable
- eGFR_{CKD-EPI} at the Analysis Start Date as a continuous variable
- LVMi at the Analysis Start Date
- previous history of cardiac, cerebrovascular, and renal clinical events (composite event) as related to Analysis Start Date
- Length of treatment for Fabry disease

If the measurements are not available, measurements prior to and closest to the Analysis Start Date will be used. In case that more than 50% of values are missing for a given covariate, it will be dropped from the analysis.

The estimate of hazard ratio for migalastat-treated/untreated along with the associated 95% CI will be calculated.

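### The cohort comes from family cascade screening, but no analysis allows for relatedness, so standard errors may be wrong, and are probably too small where genotype or treatment clusters by family

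*Protocol*

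**What the plan says.** - **How the cohort arose.** The protocol (Rationale and background) describes Fabry disease as suited to "cascade screening over at least three generations surrounding an index-patient". The next sentence applies this to the study: the Danish centre has "more than 20 years of experience of cascade screening, which has provided a patient population of 115 male and female patients".
- **What is recorded about families.** Among the inclusion variables, the Fabry-specific disease background has "Fabry family history" (yes, no or unknown) and index case (yes or no). Nothing listed links one relative to another.
- **Primary analysis.** SAP 13.1.1 fits a Cox model with sex, age, eGFR, LVMi, previous events and length of treatment as covariates. The output is described thus: "The estimate of hazard ratio for migalastat-treated/untreated along with the associated 95% CI will be calculated". No variance estimator, family or variant term, or frailty is named. SAP 13.1 states: "The analysis for the primary effectiveness endpoint will be performed at the 2-sided significance level of 0.05".
- **Other analyses.** These are the log-rank sensitivity test (13.1.1), the time-dependent Cox models (13.1.2 and 15.4), the MMRM and the t-test on eGFR slopes (13.7), and event-rate intervals by Ulm's method (7.3). None mentions family.
- **Populations.** The primary comparison is run in two sets. The Primary Effectiveness Population (5.2.1) requires a documented amenable variant and eligibility for migalastat. The Secondary Effectiveness Population (5.2.2) takes all variants.
- **Limitations.** The protocol's limitations section mentions missing data but not relatedness.

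**The concern.** Relatives found by cascade screening carry the same GLA variant. The protocol's background ties GLA mutations to enzyme activity, ties enzyme activity to phenotype and organ damage, and limits migalastat to amenable mutations. Outcome and eligibility for treatment can therefore both be correlated within families. The log-rank test and the t-test assume independent patients by construction. The Cox, MMRM and rate analyses do so unless a clustered or random-effect form is chosen, and none is.

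What is at stake is the validity of the stated 5% level and of the 95% intervals. Genotype is part of the research question and amenability is a pre-specified subgroup factor. Both are constant among relatives who share a variant, so these comparisons are the most exposed. Because no family identifier is listed, a family-level correction could not be added later from the planned data.

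**Working it through.** **The plan's own figure.** There is none to reproduce. SAP section 4 says "Sample size was not determined statistically". The figure of 115 is the whole cohort at the centre.

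**Inputs from the documents:** 115 patients; two-sided 0.05.

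**Assumptions, because the documents give no values:**
- Family size *m* is 3 to 8, which means about 115/8 ≈ 14 to 115/3 ≈ 38 families.
- The within-family correlation of outcome (ICC) is 0.05 to 0.30.
- The within-family correlation of treatment, ρ, is varied from fully shared to balanced.

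**Formulas**
- Design effect: DE = 1 + (m − 1) × ρ × ICC
- Correct interval width divided by unadjusted width: √DE
- True size of the nominal 0.05 test: 2 × [1 − Φ(1.96/√DE)]
- Balanced within families: ρ = −1/(m − 1), so DE = 1 − ICC

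**Example, m = 8, ICC 0.30, treatment shared (ρ = 1).** DE = 1 + 7 × 0.30 = 3.10 and √3.10 = 1.76. Then 1.96/1.76 = 1.11, and the true size is 26.6%.

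| m, ICC | Shared, ρ = 1 | ρ = 0.5 | Independent, ρ = 0 | Balanced |
|---|---|---|---|---|
| 3, 0.05 | DE 1.10, width ×1.05, 6.2% | DE 1.05, ×1.02, 5.6% | 5.0% | DE 0.95, ×0.97, 4.4% |
| 5, 0.10 | DE 1.40, ×1.18, 9.8% | DE 1.20, ×1.10, 7.4% | 5.0% | DE 0.90, ×0.95, 3.9% |
| 8, 0.30 | DE 3.10, ×1.76, 26.6% | DE 2.05, ×1.43, 17.1% | 5.0% | DE 0.70, ×0.84, 1.9% |

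With treatment fully shared, the effective sample size runs from 115/1.10 ≈ 105 down to 115/3.10 ≈ 37. Single-group event rates, and any factor constant within a family, behave as in the ρ = 1 column.

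**Check on censored data.** The formula is for means of equal clusters, so it was compared with a simulation of the unstratified log-rank test under the null. The settings, again assumed, were about 115 patients, families of 4 or 8, shared gamma frailty with variance 0.25 to 1.0, and 33 to 39 events on average, with 4,000 runs per setting. The observed type I error was:
- treatment shared by the family: 0.083 to 0.230
- treatment partly clustered: 0.075 to 0.137
- treatment independent of family: 0.047 to 0.052
- treatment balanced within families: 0.022 to 0.048

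The simulation shows the same pattern as the formula, including the change of direction.

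**Which case applies where**
- *Genotype and amenability comparisons, single-group rates:* ρ = 1 by construction. Intervals are too narrow if relatives' outcomes are positively correlated.
- *Migalastat versus untreated, all variants:* amenability is shared within families, so ρ is probably positive.
- *Migalastat versus untreated, amenable only:* amenability is the same for everyone and cannot separate the groups. ρ could be positive, near zero or negative.

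**The case against.** A reader might infer that every interval in the plan is too narrow and every test rejects too often. The documents do not support this. In the Primary Effectiveness Population all patients are amenable, and families spanning three generations mix sexes and ages, so relatives can fall in different treatment groups. The unadjusted interval is then about right or conservative. Contrasts that vary within families, such as sex, may behave likewise. This part of the objection stands.

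It can also be said that a shared variant is not shared severity. The protocol's background notes incomplete penetrance in heterozygous females and variable organ involvement in late-onset disease, and the cohort is "estimated 2/3 female and 1/3 male". Sex, age, eGFR, LVMi and previous events in the Cox model may absorb part of the correlation. This argues for a lower ICC, but not for assuming zero.

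Nor should 6% to 27% be read as a range of likely error rates. Family size and ICC are assumed, and treatment sharing is held at its worst value. The figure of 115 is also not the size of the primary analysis set, which is limited to amenable variants.

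Finally, the SAP is silent on the variance estimator and does not rule out a clustered one. But without a listed family identifier, clustering by family could not be carried out as planned. The GLA variant, which SAP 9.2 does list, is only a rough substitute.

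**Conclusion.** The concern holds in a conditional form. It is established that cascade screening supplied the cohort, that no analysis allows for relatedness, and that no family identifier is listed. Standard errors may therefore be wrong. They are probably too small where the compared factor clusters by family, provided relatives' outcomes are positively correlated. For migalastat versus untreated among amenable patients the direction is unknown.

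The size cannot be derived from the documents. The illustration rests on assumed family size, ICC and treatment sharing, and its upper figure of about 27% is a worst case. The direction need not be known in advance to justify a change, because family-clustered inference corrects error either way.

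**What to change.** 1. Record a coded family identifier, and report the number and size of families and how treatment is distributed within them. If pedigree links are incomplete, use the documented GLA variant as a proxy cluster in a sensitivity analysis.
2. Use family-clustered robust variance in the Cox models of SAP 13.1.1, 13.1.2 and 15.4. This leaves the hazard ratio unchanged and also covers dependence between rows from the same patient.
3. Add a family random effect to the MMRM in 13.7.
4. Replace the slope t-test, the log-rank test and the rate intervals in 7.3 with family-clustered equivalents, or report these alongside. Examples are a regression of slopes with clustered errors, a robust score test from a Cox model, and a family-level bootstrap for rates.
5. Apply a small-sample correction if families are few. Under the assumptions above there could be as few as 14.
6. Add relatedness to the protocol's limitations.

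The cost is one variable and a model option in most analyses. The documents do not say that the centre holds pedigrees, although its long experience of cascade screening makes this likely. Intervals may widen, possibly materially, and remain approximate with few families. In a small national rare-disease cohort the identifier adds some re-identification risk, so it must be coded.
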